## Convergence insufficiency study

The team will perform a clinical study comparing use of iCare by an experimental group to a standard of care (pencil pushups) control group for convergence insufficiency by patients ages 8 to 18 (inclusive). Pencil pushups are chosen as the control condition as it is the home-based therapy that is most often prescribed by both ophthalmologists and optometrists [33], [34]. Note that convergence insufficiency is rarely diagnosed and treated before age eight, thus the age range is different than for the amblyopia cohort. Informed consent will be sought from the parents or legal guardian with assent from the child. Enrollees will be assigned via a random permutation scheme to one of two groups: (1) the iCare experimental group, in which participants will be prescribed vision therapy gameplay for approximately 20 minutes per day, five days per week; and (2) a dosage-matched control group, which will be prescribed pencil pushups for 20 minutes per day, five days per week.

The primary investigational hypothesis is that improvement in positive fusional vergence base-out breakpoint (BOB) is greater for participants in the experimental group than it is for the control group. Convergence amplitudes will be measured with a base out prism bar with the patient focused on a target at 40 cm [54]. BOB will be recorded as prism magnitude at which fusion can no longer be maintained. Study investigators will also collect near point of convergence (NPC) data using an Astron International Accommodative Rule. Additionally, participants will be assessed via a CI Symptom Survey [32], a 15-item, 5-level Likert-scale. Individual responses will be assigned a value from 0-4 and summed to produce a score that can be compared to normative data [55].

The pre- to post-intervention change in BOB ( $\Delta$ BOB) at 12 weeks will serve as the primary efficacy endpoint for the Phase IIB CI study. Analysis will employ a LMM with pre- to post-intervention change in BOB as the dependent variable and intervention group (iCare or control) as the primary independent variable. Additionally, the model will include age, gender, pre-intervention BOB, and study site assignment as secondary independent variables, allowing the LMM to account for variability due to these factors and enabling factorial analysis of their impact on outcomes.

The primary null hypothesis will be that the mean of the  $\Delta$ BOB distribution is the same for the iCare and control groups, with the alternative hypothesis that the mean  $\Delta$ BOB is greater (i.e. indicating greater improvement) for the iCare group. A one-sided  $p \leq 0.025$  decision rule will be utilized to test the null hypothesis. Secondary null hypotheses will test, on a per intervention basis, whether the mean  $\Delta$ BOB of the study-population is equal to zero, with the alternative that the respective study-population  $\Delta$ BOB is greater (indicating improved functional vergence). Additionally, relationships between  $\Delta$ BOB and age, gender, and pre-intervention BOB will be systematically examined employing the LMM. NPC data will be analyzed in an identical manner.

Statistical power analysis for the CI study is based on selecting N such that there is at least an 80% probability of rejecting the primary null hypothesis when the alternative hypothesis is true. With N=50 (25 patients per group) the underlying minimum detectable difference in the mean positive fusional vergence in convergence is 7.3 prism diopters (conservatively assuming a standard deviation of 9 prism diopters [32]). In a previous randomized controlled trial, office-based CI vision therapy was found to produce a mean difference in improvement after 12 weeks of greater than 10 prism diopters [32]. The Phase IIB CI study is therefore sufficiently powered. To account for potential dropouts, up to 64 total patients will be consented into the CI study.

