## **ICARE PROTOCOL AND ANALYSIS PLAN**

**Study Title: A New Approach to Vision Therapy Based on Naturalistic 3-D Computer Gaming**

**Study ID: ICARE2B**

**Document Date: 8/30/2023**

**NCT number: NCT03066063**

The research team will execute two concurrent studies within a common framework. The first will compare iCare to standard of care occlusion therapy (patching) for amblyopia in patients ages 4 to 18 (inclusive). The second will compare iCare to a standard of care for home-based CI therapy (pencil pushups) for convergence insufficiency patients ages 8 to 18 (inclusive). In the context of this study, the term iCare refers to either the amblyopia or CI video game module as appropriate for the respective study group.

Both the amblyopia and CI studies will follow the same basic approach. Each study will last 12 weeks, and participants will return for follow-up visits at Weeks 4, 8, and 12. Patients will receive full visual exams to establish baseline data upon enrollment, and again at Week 12 to record post-treatment data. During the interim visits (Weeks 4 and 8), patients' visual function will be assessed by a study optometrist, and any changes to the iCare configuration will be addressed as needed. As iCare is a home-based therapy, participants must have access to a personal computer and the Internet. For patients without access, the research team will provide loaner computers and/or pre-paid Verizon wireless mobile hotspots for Internet connectivity.

The proposed clinical studies will use the provider-as-investigator model that involves a minimum of 10 study sites and approximately 100 participants (see statistical power analysis below). With this approach, the research team will recruit optometry and vision therapy clinics and practices from around the country to support study execution under the training, guidance, and supervision of the iCare team. UND will serve as the "coordinating center" [48], enrolling, training, and overseeing the study sites and providing Institutional Review Board (IRB) governance. The UND team has experience in successfully serving in this multi-center coordination role in related research (see Biosketches). Enrolled providers (known hereafter as *investigator-providers*) will, in turn, recruit participants from their own patient rosters. This model serves several important purposes:

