### **Amblyopia study**

Children (ages 4-18) with amblyopia and meeting study inclusion/exclusion criteria will be recruited according to IRB-approved procedures. Informed consent will be sought from the parents or legal guardian with assent from the child. Enrollees will be randomized to one of two groups. A standard of care group will be prescribed patching for two or six hours per day, seven days per week. Standard of care group participants with best-corrected vision worse than 20/200 in their amblyopic eye will be prescribed six hours of patching daily, while participants whose best-corrected visual acuity is 20/200 or better will be prescribed two hours of patching daily. Participants assigned to an experimental group will play iCare vision therapy games for approximately 20 minutes per day, five days per week. Assignments will be made via a block randomization scheme based on a random permutation. With regards to age, it is expected that amblyopia patients between ages 4 to 6 years may experience up to one line (0.1 logMAR) greater improvement than those over 6 years of age [51]. For this reason, assignments within the amblyopia patient cohort will be age-balanced.

The primary investigational hypothesis is that the improvement in best-corrected visual acuity for participants in the iCare experimental group will not be inferior to the level of improvement observed in the standard of care (patching) group. An ETDRS (Early Treatment Diabetic Retinopathy Study) logMAR (logarithm of the minimum angle of resolution) chart [52] will be used as the primary assessment of visual acuity (VA). To reduce test-retest-variability, scoring will be based on an interpolated logMAR value (single-letter score) based on all measurements via the formula,  $VA = 1.1 - T_c L_v$ , where  $T_c$  is the total number of correctly read letters and  $L_v$  is the logMAR value of each letter on the chart (0.02 for ETDRS) [53]. In children 4-6 years old, a Lea Symbols chart [46] will also be used, with the best VA score from the two tests used for primary analyses.

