The pre- to post-intervention change in best-corrected vision ( $\Delta$  logMAR) at 12 weeks will serve as the primary efficacy endpoint. In terms of hypothesis testing, the primary null hypothesis will correspond to a non-inferiority test in which the null hypothesis will be that the mean of the  $\Delta$  logMAR distribution for the iCare experimental study population is greater than that of the patching experimental study population (indicating inferior average outcome), while the alternative hypothesis will be that the mean  $\Delta$  logMAR for the iCare experimental study population is equal to or more negative than the mean  $\Delta$  logMAR patching experimental study population (indicating iCare therapy is non-inferior to patching therapy with respect to improving visual acuity). The null hypothesis will be rejected if the upper 95% confidence limit for the between-group difference (i.e. iCare – patching) in mean  $\Delta$  logMAR does not exceed the non-inferior threshold of one line on an ETDRS chart (approximately 0.1 logMAR). Analysis will be performed by way of a linear mixed model (LMM) in which the pre- to post-intervention change ( $\Delta$  logMAR) will be the LMM dependent variable, while the intervention (iCare vs. patching) will serve as the primary LMM independent variable and patient age, gender, pre-intervention logMAR in the amblyopic eye, and logMAR in the fellow eye will all serve as secondary LMM independent variables. These secondary variables will be utilized to adjust for any between-intervention disparities in age, gender, pre-intervention logMAR in the amblyopic eye, and logMAR in the fellow eye. Inclusion of these secondary independent variables in LMM will also allow assessment of the impacts on these characteristics on outcomes. Additionally, a stratification variable “study site” will be incorporated into the LMM as a random-effect to account for within study-site measurement correlation as well as between study-site variability.

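### Does the convergence insufficiency model need to say that study site is a random effect?

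*Combined protocol and SAP*

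**What the plan says.** In the section on the convergence insufficiency study, the primary analysis is a linear mixed model with the 12-week change in base-out breakpoint (BOB) as outcome and intervention group as the main predictor. Age and gender are listed next, then "pre-intervention BOB, and study site assignment as secondary independent variables, allowing the LMM to account for variability due to these factors". The same sentence mentions a factorial analysis of the impact of these variables. A later paragraph names age, gender and pre-intervention BOB as the relationships to be examined with the model and leaves site out. Near point of convergence is analyzed the same way.

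The section on the amblyopia study keeps two roles apart. Age, gender, baseline acuity in the amblyopic eye "and logMAR in the fellow eye will all serve as secondary LMM independent variables", and site "will be incorporated into the LMM as a random-effect to account for within study-site measurement correlation as well as between study-site variability".

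On assignment, the CI section says only that enrollees are "assigned via a random permutation scheme to one of two groups". The amblyopia section says that "assignments within the amblyopia patient cohort will be age-balanced". The opening overview plans for "a minimum of 10 study sites and approximately 100 participants" over the two studies.

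**The concern.** The amblyopia section gives the label of secondary independent variable to its patient-level covariates and says of them: "Inclusion of these secondary independent variables in LMM will also allow assessment of the impacts on these characteristics on outcomes". If that usage carries over, putting site under the same label in the CI section makes it a fixed factor. Fifty completers over 10 sites is 5 per site, and 10 sites need 9 indicators. Fixed site terms discard the treatment comparison between sites and use 9 degrees of freedom.

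Two things would be at stake. The two models give different estimates and standard errors for one decision at one-sided 0.025, so the choice should not be open once data are seen. The fixed version would also be less precise than the model the sponsor already uses for amblyopia at the same sites.

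**Working it through.** **The plan's own figure.** Inputs from the CI section: 25 per group, SD 9, 80% power, one-sided 0.025. With 48 degrees of freedom, the detectable difference is about (t₀.₉₇₅ + t₀.₈₀) × SD × √(2/25) = (2.011 + 0.849) × 9 × 0.2828 = 7.28 prism diopters. This reproduces the stated 7.3. The calculation has no site term, so it does not show which site model was in mind.

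**Which reading fits the text.**
- For fixed: site shares a list with patient covariates, and that list is linked to factorial analysis.
- For random: the model is called a mixed model, each patient contributes one change score, and no other listed term could be random. With site fixed, nothing mixed would remain. The later list of relationships to be examined omits site. The stated purpose of accounting for variability matches the purpose given for the random effect in the amblyopia study.

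A random site effect is the more likely intent.

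**Cost of the other reading.** Assumptions: 50 completers, 25:25, 10 sites, total SD 9, three uninformative covariates. The documents give no site ICC, so 0, 0.1, 0.2 and 0.3 are shown.

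Hand check for 5 per site, arms not balanced by site:
- The treatment indicator has sum of squares 50/4 = 12.5 on 49 degrees of freedom. The three covariates leave on average 46/49 of it. Adding 9 site indicators leaves 37/49.
- At ICC 0 the variance ratio, fixed over random, is about 46/37 = 1.24.
- At ICC ρ, between-site information carries weight w = (1 − ρ)/(1 + 4ρ) = 1, 0.643, 0.444, 0.318. The ratio is about 1 + 9w/37 = 1.24, 1.16, 1.11, 1.08.

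Hand check for arms balanced within sites (3:2 or 2:3): within-site sum of squares is 10 × (3 × 2/5) = 12 of 12.5. At ICC 0, before covariates, the ratio is 12.5/12 = 1.04.

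Simulated allocations average slightly higher:

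| Variance ratio, fixed/random, 5 per site | ICC 0 | 0.1 | 0.2 | 0.3 |
|---|---|---|---|---|
| Not balanced by site | 1.26 | 1.17 | 1.12 | 1.09 |
| Balanced by site | 1.06 | 1.04 | 1.03 | 1.02 |

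Detectable difference and power with allocation not balanced and site sizes random (random-effect power uses Kenward-Roger):

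| | ICC 0 | 0.1 | 0.2 | 0.3 |
|---|---|---|---|---|
| Detectable difference, fixed | 8.5 | 8.0 | 7.6 | 7.1 |
| Detectable difference, random | 7.5 | 7.4 | 7.1 | 6.7 |
| Power at 10 diopters, fixed | 91% | 93% | 96% | 97% |
| Power at 10 diopters, random | 95% | 96% | 97% | 98% |

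Hand check at ICC 0, fixed: the standard error is 9/√(12.5 × 37/49) = 2.93, and (2.028 + 0.852) × 2.93 = 8.4.

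**Validity.** In 10,000 simulated trials per ICC, one-sided error was 2.2 to 2.5% with fixed site terms, 2.5 to 2.8% with a random intercept and residual degrees of freedom, and 2.0 to 2.6% with Kenward-Roger. None departs materially from 2.5%.

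**The case for a change.** The strongest case for a change is that a primary model which can be fitted in two ways should be settled before unblinding, and that one sentence would do it. Ten sites is also a minimum. At 15 sites with unbalanced allocation the variance ratio rises to 1.48/1.36/1.27/1.21 and the fixed-site detectable difference to 9.3/8.8/8.3/7.7 (ICC 0/0.1/0.2/0.3). At the 7.3-diopter planning difference with 10 equal sites and unbalanced allocation, power is 67 to 75% with fixed terms against 77 to 81% with a random intercept (ICC 0 to 0.2).

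Part of this stands. The CI section does omit a phrase that the amblyopia section has, and the precision loss is real if site is fitted as fixed. But the larger losses need three things together: the less likely reading, low site correlation, and arms not balanced within sites. Balance cannot be ruled out, since the amblyopia analysis introduces site with the words "Additionally, a stratification variable", although neither assignment paragraph mentions it. Even 9.3 lies below the 10-diopter benchmark that the plan uses to judge its power.

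Nor is a random effect plainly better if the sponsor chose fixed terms on purpose to look at site. With about 10 sites the variance is poorly estimated: the REML estimate was zero in 56/28/12/5% of simulated trials at ICC 0/0.1/0.2/0.3, and site-specific fixed estimates would be given up. Requiring Kenward-Roger for CI alone would create a new difference from the amblyopia model, which names no such method.

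**Conclusion.** This is missing detail that analysts would fill sensibly. The CI section leaves the role of site unstated, but a mixed model with one outcome per patient points to a random site effect, as in the amblyopia study. If fixed terms were fitted instead, the test would remain valid, with error near 2.5%. The variance cost would be about 2 to 6% with arms balanced within sites and about 9 to 26% without, at 10 sites and an assumed ICC of 0.3 down to 0. The conclusion that the study is sufficiently powered against 10 diopters holds either way. Near point of convergence shares the wording, and the same reasoning applies. These sizes rest on an assumed ICC, uninformative covariates and 10 sites; more sites would enlarge the loss under the fixed reading. No change to the plan is called for.

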Secondary analyses will test, on a per intervention basis, the null hypotheses that the mean  $\Delta$  logMAR for each treatment group mean (iCare and patching) is greater than or equal to zero, with the alternative hypothesis that the mean  $\Delta$  logMAR of the respective study-population is less than zero (indicating improved acuity associated with the respective treatment between pre-/post-testing). Additionally, systematic relationships between  $\Delta$  logMAR and age, gender and per-intervention logMAR will be examined in secondary factorial analysis.

Statistical power analysis for the amblyopia study is based on selecting N such that there is at least an 80% probability of rejecting the primary null hypothesis (when the alternative hypothesis is true) that the mean  $\Delta$  logMAR of the iCare experimental study population minus the mean  $\Delta$  logMAR of the patching experimental study population exceeds the non-inferior threshold. Assuming a standard deviation in acuity improvement between subjects of approximately 2 lines on the ETDRS chart (0.2 logMAR – consistent with observed variability in previous studies [51], [26]), at least 50 patients must complete the amblyopia study (25 each in the iCare and patching groups) to achieve adequate statistical power. Thus, if the true mean of the  $\Delta$  logMAR distribution for the iCare group is less than or equal to (better than) the true mean of the  $\Delta$  logMAR distribution for the patching group, there is an 80% chance that the null hypothesis of iCare amblyopia therapy inferiority to patching amblyopia therapy will be correctly rejected. To account for potential dropouts, up to 64 total patients will be consented into the amblyopia study.

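### Relating change in logMAR, BOB or NPC to the baseline of the same measure is biased by measurement error towards the reading that worse patients improve more

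*Combined protocol and SAP*

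**What the plan says.** **Convergence insufficiency study.** "Analysis will employ a LMM with pre- to post-intervention change in BOB as the dependent variable". Pre-intervention BOB is among the secondary independent variables, which serve two purposes: "allowing the LMM to account for variability due to these factors and enabling factorial analysis of their impact on outcomes". Among the secondary analyses, relationships between change in BOB and "age, gender, and pre-intervention BOB will be systematically examined employing the LMM". For the near point of convergence, "NPC data will be analyzed in an identical manner".

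**Amblyopia study.** The model for change in logMAR includes the amblyopic eye's pre-intervention logMAR. Adjustment for imbalance is one stated purpose. The other is this: "Inclusion of these secondary independent variables in LMM will also allow assessment of the impacts on these characteristics on outcomes". The secondary analyses add that relationships between change and "age, gender and per-intervention logMAR will be examined in secondary factorial analysis". I read the prefix *per* as a slip for *pre*.

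**Measurement error.** The Amblyopia study section names test-retest variability as the reason for single-letter acuity scoring, but gives no size for it. Neither section gives a reliability, a replicate baseline, a comment on regression to the mean, or an arm-by-baseline interaction.

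**The concern.** The change score is post minus pre, and pre is also the predictor to be interpreted. A patient whose baseline is measured too low by chance has a low predictor value and an inflated change; one measured too high has the reverse. This alone produces a negative slope.

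The negative slope has the same clinical reading for all three measures. Low BOB is worse and should rise. High logMAR and high NPC are worse and should fall. Each analysis therefore leans towards worse patients improving more, and agreement among them could be taken for confirmation when all three share one artefact. Adjusting for age, gender and site does not remove it.

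At stake is a planned secondary conclusion about which patients improve most. A baseline slope pooled over arms also does not show whether the difference between iCare and control varies with severity.

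**Working it through.** **1. The plan's own figure.** The CI section gives 25 per group, SD 9 prism diopters, one-sided 0.025, 80% power and a minimum detectable difference of 7.3. The normal approximation gives (1.960 + 0.842) × 9 × √(2/25) = 7.13. The noncentral t with 48 df gives 7.28, and power of 80.2% at 7.3. The figure reproduces. I take 9 as the SD of change, which the text does not state.

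**2. Inputs.** From the documents: 50 patients per study, SD of change 0.2 logMAR (Amblyopia study) and 9 prism diopters (CI study). Assumed, because the documents give neither: the true baseline SD (s_b) and the SD of measurement error (s_e). There are no NPC figures, so the mechanism applies to NPC but its size cannot be calculated.

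**3. Expected slope with no true relation.** Observed baseline = true + error, and true change is independent of true baseline. Then

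slope = -s_e² / (s_b² + s_e²) = -(1 - reliability).

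Example: s_b = 4, s_e = 2 gives -4/20 = -0.20.

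**4. False positives.** I simulated 4,000 trials per setting with N = 50, change regressed on arm and baseline, and a two-sided 5% test of the baseline slope. Age, gender and site were left out.

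| Measure | s_b | s_e | Formula slope | Simulated slope | Rejections |
|---|---|---|---|---|---|
| logMAR | 0.30 | 0.05 | -0.027 | -0.026 | 5.9% |
| logMAR | 0.25 | 0.07 | -0.073 | -0.073 | 10.2% |
| logMAR | 0.25 | 0.10 | -0.138 | -0.139 | 25.6% |
| logMAR | 0.20 | 0.10 | -0.200 | -0.204 | 35.4% |
| BOB | 4 | 2 | -0.200 | -0.207 | 11.4% |
| BOB | 4 | 3 | -0.360 | -0.360 | 27.6% |
| BOB | 3 | 3 | -0.500 | -0.494 | 37.4% |

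Repeat runs agreed closely; the largest value was 39%.

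**5. A wider range.** These are the chances of a significant slope in the worse-improve-more direction (nominal 2.5%), by reliability and observed baseline SD, with 20,000 trials per setting.

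| Measure, baseline SD | 0.95 | 0.90 | 0.80 | 0.70 |
|---|---|---|---|---|
| BOB, 4 | 4% | 5% | 9% | 14% |
| BOB, 6 | 4% | 7% | 15% | 29% |
| BOB, 9 | 5% | 10% | 28% | 56% |
| logMAR, 0.2 | 5% | 10% | 29% | 57% |
| logMAR, 0.3 | 7% | 18% | 56% | – |

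The dash marks a setting where the assumed error alone would exceed the stated SD of change. Hand check for BOB, SD 9, reliability 0.80: the correlation is -0.20 × 9/9 = -0.20, so the t statistic centres near -0.20 × √47 / √(1 - 0.04) = -1.40. Against a critical value of -2.01, Φ(-2.01 + 1.40) = Φ(-0.61) ≈ 27%.

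**6. Treatment comparison.** In the CI setting (reliability 0.7 to 0.9, baseline SD 6 or 9), the baseline-adjusted treatment test keeps its one-sided type I error at 2.4% to 2.6%.

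**7. Alternatives, same settings as step 6.** The slope against zero rejects in 7% to 56% of trials. The slope against -(1 - reliability) rejects in 4.8% to 5.2%, and the arm-by-baseline interaction in 4.8% to 5.1%.

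**8. Oldham's method (change against the mean of pre and post).** Its slope is zero only if pre and post variances are equal. If true change varies between patients with variance v, independently of baseline, the slope is (v/2) / (s_b² + v/4 + s_e²/2). For BOB with s_b = 4 and s_e = 2, v = 81 - 2 × 4 = 73, and the slope is 36.5 / (16 + 18.25 + 2) = +1.01. In the settings of step 4 it rejects in 23% to 52% of trials for logMAR and 99% to 100% for BOB, with the opposite sign.

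**The case against.** The plan says only that relationships will be examined. It states no alpha, no test against zero and no expected conclusion for them. A reader might infer that the trial will report that worse patients improve more. The documents do not support that: the bias in the slope is certain whenever baseline error exists, but a significant false finding is not. In every setting of step 4 most trials would not show one. The size rests on assumed inputs, and single-letter scoring points towards the lower end for acuity. This all stands, and it limits the claim to bias of uncertain size.

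A reader might also infer that the problem is worse in the CI study because enrolled patients have a narrow range of BOB. The text gives no BOB entry threshold or baseline SD. The inference also needs a fixed error SD; at fixed reliability a narrower baseline lowers the false-positive rate (9% at SD 4 against 28% at SD 9, reliability 0.80). Nor does any section tie these analyses to labelling or patient selection.

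Finally, an interaction answers a different question from the one planned. That is fair, so the fix also keeps a route to the overall relation. The word *factorial* might be taken to include an interaction with intervention, but no such term is specified.

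**Conclusion.** The concern holds for the secondary interpretation of the baseline coefficient. With no true relation its expected value is -(1 - reliability), and read against zero it favours the conclusion that worse patients improve more, for logMAR, BOB and NPC alike. With 50 patients and the stated SDs of change, false positives at a nominal two-sided 5% run from about 6% to 39% in the settings of step 4. They exceed 50% where reliability is low relative to a wide baseline spread. These figures depend on assumed reliability and baseline SD, and on reading 9 prism diopters as the SD of change.

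A reader might infer that baseline should leave the model or that the primary comparisons are compromised. Neither follows: the randomised treatment contrast keeps its error rate, and adjusting for baseline is sound.

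**What to change.** In both study sections:

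- State that the baseline value of the outcome measure is an adjustment covariate, and that its coefficient will not be tested against zero or read as the effect of severity on improvement.
- If differential benefit by severity is of interest, pre-specify an arm-by-baseline interaction for logMAR, BOB and NPC, labelled exploratory.
- If the overall relation is wanted, use a slope corrected for measurement error (Blomqvist) with a stated test-retest reliability and a sensitivity range around it.
- Do not use Oldham's method, for the reason in step 8.

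Age and gender analyses stay as they are. The cost is SAP wording, one extra model term per measure and, for the corrected slope, a reliability value that the documents do not now contain. No sample size changes. The drawback is that the interaction has low power at 25 per arm, so a null result would say little.

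### Does analysing NPC in the same way as BOB put the one-sided NPC tests in the wrong tail?

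*Combined protocol and SAP*

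**What the plan says.** All of this is in the section Convergence insufficiency study of the combined protocol and SAP.

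- **Primary analysis.** Change in BOB at 12 weeks is the primary endpoint: "Analysis will employ a LMM with pre- to post-intervention change in BOB as the dependent variable". On covariates, "the model will include age, gender, pre-intervention BOB, and study site assignment as secondary independent variables".
- **Between-group test.** The alternative is that mean change in "BOB is greater (i.e. indicating greater improvement) for the iCare group". The level is given as "A one-sided $p \leq 0.025$ decision rule will be utilized to test the null hypothesis".
- **Within-arm tests.** The null is zero mean change. The alternative is that the change in "BOB is greater (indicating improved functional vergence").
- **NPC.** On measurement: "Study investigators will also collect near point of convergence (NPC) data using an Astron International Accommodative Rule". On analysis, the only statement is "NPC data will be analyzed in an identical manner".

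The document gives NPC no sign convention, no tail, no baseline covariate of its own, and no SD or effect size.

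**The concern.** BOB is the prism strength at which fusion breaks, so an increase is a gain. NPC is a near point read on a rule. The documents do not say that smaller is better, but the meaning of the term implies it: a nearer point is better convergence. If change is Week 12 minus baseline, improvement in NPC is negative. A reader who copies the BOB procedure word for word would then test whether NPC moved further away with iCare. A real benefit could hardly ever be significant, and a real harm could be reported as success. This would apply both between groups and within each arm.

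The same literal copying would leave baseline BOB in the NPC model where baseline NPC belongs, losing the precision that the outcome's own baseline provides.

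**Working it through.** **1. Reproduce the plan's own figure.** Inputs from the CI power paragraph: 25 per group, SD 9 prism diopters, 80% power; one-sided alpha 0.025 comes from the decision rule. The standard error of the difference is 9 × √(2/25) = 2.546. With the noncentral t on 48 degrees of freedom, power reaches 80% at a difference of 7.28, which rounds to the stated 7.3. At 7.3 itself, power is 80.2%. So the BOB design is a one-sided 0.025 t test, and the same test can be evaluated for NPC.

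**2. What a reversed tail would cost.** The documents give no SD or effect for NPC, so standardized benefits *d* of 0.2, 0.5 and 0.8 SD are assumed as a range. The noncentrality is d/√(2/25): 0.71, 1.77 and 2.83. The model covariates and site are ignored.

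| True benefit of iCare | Rejects, improvement tail | Rejects, literal greater on raw change |
|---|---|---|
| 0.2 SD | 10% | 0.4% |
| 0.5 SD | 41% | 0.01% |
| 0.8 SD | 79% | 0.0001% |

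By symmetry, if iCare were 0.5 SD worse, the reversed test would favour it 41% of the time. Within one arm (n = 25, assumed fall of 0.5 SD, noncentrality 0.5 × √25 = 2.5), the figures are 67% and about 0.0006%. With no true difference, either tail rejects 2.5% of the time.

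These figures describe any one-sided test pointed the wrong way. Whether they apply here depends on whether the plan points it that way.

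**3. Does the text specify the wrong tail?**

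- Each BOB alternative comes with a gloss that explains greater as improvement. The CI hypothesis itself is also framed as greater improvement with iCare. What carries over to NPC is the same mixed model, the same 0.025 level and a test for improvement. Reaching the wrong tail requires keeping the word and dropping its explanation.
- The section Amblyopia study handles an outcome where lower is better. There the favourable between-group direction is the more negative mean change in logMAR, and the within-arm alternatives are below zero, explained as improved acuity. These authors set direction by clinical meaning.

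**4. Does the text specify the wrong baseline?** The CI model is change in BOB adjusted for pre-intervention BOB. The amblyopia model is change in logMAR adjusted for pre-intervention logMAR in the amblyopic eye, among other covariates. The pattern is change in an outcome adjusted for its own baseline. Putting NPC in place of BOB throughout gives baseline NPC. Baseline BOB survives only if the substitution is made in the dependent variable and not in the covariate.

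**The case for a change.** The strongest case for a change is that a one-sided test must have its tail fixed before the data are seen. The plan fixes none for NPC, and the only direction it supplies by reference is, taken literally, the unfavourable one. An analyst who picked the tail after seeing the data would double the level from 2.5% to 5% (2 × 0.025). The care taken over logMAR shows that the authors regarded direction as something to write down, and NPC needed the same care. A sentence would cost nothing.

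Part of this stands. The direction is unstated, and a clarifying sentence would do no harm. But the tail is not open to choice from the data: the meaning of a near point settles which way is better before any result exists, and the glosses settle that the test is for improvement. An analyst who reported a receding near point as success would have to ignore both, as well as the group means.

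**Conclusion.** The concern does not call for a change. The plan leaves a detail unstated, and analysts would fill it in the only sensible way: test NPC in the direction of improvement, adjusted for baseline NPC. The contrast of 41% with 0.01% is correct arithmetic under an assumed effect of 0.5 SD and a simple t test, but it belongs to a reading the text does not support.

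The stakes are also limited. NPC is a supporting outcome with no power calculation, and no stated trial conclusion turns on it. The primary BOB comparison, the one-sided 0.025 level, the sample size of 50 and the detectable difference of 7.3 prism diopters stay as they are under any reading. The conclusion rests on one inference from outside the text, that a smaller NPC is better, which follows from the name of the measure.
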